1. LIST OF ABBREVIATIONS

AE	Adverse Event
ALT	Alanine Aminotransferase
AST	Aspartate Aminotransferase
BMI	Body Mass Index
CDC	Centers for Disease Control and Prevention
CTMS	Clinical Trial Management System
DMC	Data Monitoring Committee
ECG	Electrocardiogram
eCRF	Electronic Case Report Form
EDC	Electronic Data Capture
EN	Enteral Nutrition
EOS	End of Study
EOT	End of Treatment
GI	Gastrointestinal
HLGT	Higher Level Group Term
ICH	International Conference on Harmonisation
ITT	Intention-to-Treat
MedDRA	Medical Dictionary for Regulatory Activities
MOS	Months
NA	Not Applicable
PD	Pharmacodynamics
PK	Pharmacokinetic
PN/IV	Parenteral Nutrition/Intravenous Fluid
PP	Per Protocol
PT	Preferred Term
SAE	Serious Adverse Event
SAF	Safety
SAP	Statistical Analysis Plan
SBS	Short Bowel Syndrome
SE	Standard Error
SI	Standard International
SOC	Standard of Care
TEAE	Treatment-Emergent Adverse Event
TESAE	Treatment-Emergent Serious Adverse Event
UGI/SBFT	Upper GI series with Small Bowel Follow-Through
ULN	The soul insit of Name of
	Upper Limit of Normal
WHODD YRS	WHO Drug Dictionary Years

Document: T:\Shire\Teduglutide\XXA39799\Biostatistics\Documentation\SAP\SHP633-302_SAP_Final

1.0_17Apr2019.docx

Author: Version Number: Final 1.0 Version Date: 17Apr2019

Template No: CS_TP_BS016 Revision 4

Effective Date: 01Apr2016

Copyright © IQVIA. All rights reserved.

2. Introduction and Background Information

This document describes the rules and conventions to be used in the presentation and analysis of efficacy and safety data for Protocol SHP633-302. It describes the data to be summarized and analyzed, including specifics of the statistical analyses to be performed. Pharmacokinetic analysis will be detailed in a separate analysis plan.

This statistical analysis plan (SAP) is based on protocol amendment 4, dated 12 June 2018.

2.1. STUDY DESIGN

This will be an open-label, 24-week study, in which subjects will receive 0.05 mg/kg/day of teduglutide. The study population will include 2 cohorts: infants 4-<12 months corrected gestational age and children 1-15 years of age.

All subjects will be screened for a minimum of 2 weeks prior to start of treatment to verify the requirements for nutritional support for each subject and to ensure adherence to eligibility parameters. Attempts should be made to limit the screening period to 4 weeks.

After screening, the 24-week treatment period will consist of visits at baseline, weekly for the first 2 weeks, and then every other week through week 12. For the remainder of the treatment period, visits at the sites will be conducted every 3 weeks. Scheduled telephone contacts will be made on all other weeks during the treatment period. At all site visits and during telephone contacts, safety will be monitored and nutritional support will be reviewed and adjusted as needed. The end of study (EOS) visit will be scheduled at week 28, 4 weeks following end of treatment (EOT). Weekly telephone contact will be made during the interim weeks from EOT to EOS to monitor safety and any changes in nutritional support.

To maintain consistency across all centers, all attempts should be made to follow the nutritional support adjustment guidelines and weaning algorithms (developed with SBS expert input and provided in the protocol) for decisions regarding parenteral nutrition/intravenous fluids (PN/IV) support reduction and advances in enteral feeds based on weight gain, urine, and stool output in the setting of clinical stability. Any departure from the nutritional support adjustment guidelines and weaning algorithms will not constitute a protocol deviation.

A schematic representation of the study design is displayed in Figure 1. The study schedule of events can be found in Table 1 and Table 2 of the protocol.

Figure 1 Study Diagram

[figure not shown]
Document: T:\Shire\Teduglutide\XXA39799\Biostatistics\Documentation\SAP\SHP633-302 SAP Final

1.0_17Apr2019.docx

Author: Version Number: Final 1.0 Version Date: 17Apr2019

Template No: CS_TP_BS016 Revision 4 Reference: CS_WI_BS005

Effective Date: 01Apr2016

2.2. OBJECTIVE

The objective of this clinical study is to evaluate the safety, tolerability, efficacy and pharmacodynamics, and pharmacokinetics of teduglutide in pediatric subjects (4 months through 15 years of age) with short bowel syndrome (SBS) who are dependent on parenteral support.

2.2.1. EFFICACY/PHARMACODYNAMIC ASSESSMENTS

The efficacy/pharmacodynamic endpoints include:

- Change (absolute and percent change) from baseline in PN/IV support (volume and calories), citrulline (only for the cohort of children 1-15 years of age), and enteral nutritional support (volume and calories), separately, at each visit
- Reduction in PN/IV volume of at least 20% at week 24 (or EOT) compared to baseline
- 100% reduction in PN/IV volume (complete weaning of PN/IV support) at week 24 (or EOT) compared to baseline
- ≥20% reduction in PN/IV volume at each visit
- Change (absolute and percent change) from week 24 (or EOT) in PN/IV support (volume and calories), citrulline (only for the cohort of children 1-15 years of age), and enteral nutritional support (volume and calories), separately, to week 28 (or EOS)
- Change in hours per day and days per week of PN/IV support

2.2.2. SAFETY ASSESSMENTS

Safety and tolerability will be assessed by evaluating the following:

Document: T:\Shire\Teduglutide\XXA39799\Biostatistics\Documentation\SAP\SHP633-302 SAP Final

1.0_17Apr2019.docx

Version Number: Final 1.0
Version Date: 17Apr2019

Template No: CS TP BS016 Revision 4

Effective Date: 01Apr2016

Author:

Reference: CS_WI_BS005

- Adverse events, including those pertaining to GI symptoms.
- Physical examinations, including body weight, height (or length), head circumference (up to 36 months of age), and trends on growth charts
- Vital signs, including temperature, heart rate, blood pressure
- Electrocardiograms (ECGs)
- Laboratory safety data (ie, biochemistry, hematology, coagulation, urinalysis)
- Urine output
- Fecal output (by volume or number of bowel movements per day)
- Antibodies to teduglutide
- For children 1 to 15 years of age: GI-specific testing including colonoscopy or sigmoidoscopy, abdominal ultrasound, fecal occult blood testing, upper GI series with small bowel followthrough (UGI/SBFT)
- For infants 4 to <12 months corrected gestational age: UGI/SBFT

3. DETERMINATION OF SAMPLE SIZE

The sample size is determined based on enrollment feasibility of this orphan population in children in Japan, rather than power calculation.

4. Unblinding Procedures

No unblinding procedures apply as this is an open-label study.

5. DATA MANAGEMENT

IQVIA is responsible for data management activities for this study. Details about data management, including the eCRF design, the EDC system, data validation and discrepancy management, reconciliation of data from different sources, and electronic data transfer, are included in the Data Management Plan for this study.

6. STATISTICAL/ANALYTICAL ISSUES

6.1. GENERAL METHODOLOGY

All statistical procedures will be completed using SAS version 9.4 or later.

Document: T:\Shire\Teduglutide\XXA39799\Biostatistics\Documentation\SAP\SHP633-302 SAP Final

1.0 17Apr2019.docx

Author: Version Number: Final 1.0 Version Date: 17Apr2019

Template No: CS_TP_BS016 Revision 4 Reference: CS_WI_BS005

Effective Date: 01Apr2016

Copyright © IQVIA. All rights reserved.

Due to the limited size of the study population descriptive statistics will be used with a goal of summarizing the sample which discourages the use of inferential statistics. Accordingly, no claims of significance will be made for any of the data.

Continuous variables, including those assessed on a discrete scale, will be summarized using descriptive statistics including number of subjects, mean, median, standard deviation, maximum, and minimum. Standard errors (SE) will be displayed for the efficacy tables, and body weight, height (or length), BMI, head circumference and weight for length. For categorical variables, descriptive statistical summaries will include number of subjects and percentages.

For summary purposes, the baseline value will be defined as the last available pre-dose value. Scheduled visits will be summarized as provided in the electronic case report forms (eCRFs). An End of Treatment (EOT) time point, defined as the last determination of endpoint or last available measurement after the date of first dose during the 24-week treatment period will be analyzed in addition to the scheduled visits. Similarly, an End of Study (EOS) time point will be defined as the last determination of endpoint or last available measurement after the EOT during the 4-week follow-up period. Unscheduled measurements will not be included in by-visit summaries, but can contribute to the EOT/EOS value where applicable.

Study Day will be calculated as follows:

- If the date of the evaluation is on or after the first day of study medication then: Study Day = (date of the evaluation – first day of study medication) + 1.
- If the date of the evaluation is prior to the first day of study medication then: Study Day = (date of the evaluation – first day of study medication).

Datasets and listings will include data collected at unscheduled visits. Data collected at unscheduled visits will not be included in summaries by timepoint or visit unless specified otherwise.

Data will be analyzed and presented by subject cohorts:

- Infants: 4-<12 months corrected gestational age
- Children: 1-15 years of age

The corrected gestational age as captured on the demographics page of the eCRF will be used to determine the cohort a subject belongs to, i.e., if the corrected gestational age is <12 months, the subject will be in the infant cohort. The infant cohort will be analyzed in a manner analogous to the cohort of children 1-15 years of age unless specified otherwise.

Analyses will be done for all subjects, and subset of subjects who began treatment after protocol amendment 3.0. Main conclusions will be based on subjects who began treatment after implementation of protocol amendment 3.0.

Document: T:\Shire\Teduglutide\XXA39799\Biostatistics\Documentation\SAP\SHP633-302 SAP Final

1.0_17Apr2019.docx

Template No: CS_TP_BS016 Revision 4

Effective Date: 01Apr2016

Author:

Version Date: 17Apr2019

Version Number:

Reference: CS_WI_BS005

Final 1.0

6.2. ADJUSTMENTS FOR COVARIATES/PROGNOSTIC VARIABLES

No adjustments for covariates are planned in the statistical analyses.

6.3. HANDLING OF DROPOUTS OR MISSING DATA

All subjects in the analysis population defined in Section 7 will be included in the associated analyses.

No imputation for missing data (e.g., last observation carried forward [LOCF]) will be applied except for the partial dates for adverse events and prior/concomitant medications.

Details on how to handle partial dates for adverse events and prior/concomitant medications are described below.

Complete dates will be imputed from partial dates of adverse events and medications solely for the purpose of defining treatment emergence for adverse events and prior/concomitant status for medications (Imputed dates will not be presented in the listings). Dates will be defined using the hierarchy of derivations below.

Adverse event or medication start date (references to month and year are the month and year of the start date):

- 1. If year and month are known, and it is the month and year of the first dose date, use the first dose date.
- 2. If year and month are known, and it is not the month and year of the first dose date, use the first day of the month.
- 3. If only year is known, and it is the year of the first dose date, use the first dose date.
- 4. If only year is known, and it is not the year of the first dose date, use the first day of the year (1st January).
- 5. Should any of the previous start dates created be after a complete stop date provided, use the stop date as the start date, instead of the date that would otherwise be created.
- 6. For medication start date, if "Before Informed Consent" is ticked then use the date of informed consent.
- 7. Otherwise, if start date is unknown leave as missing.

Adverse event or Medication stop date (references to month and year are the month and year of the stop date):

Document: T:\Shire\Teduglutide\XXA39799\Biostatistics\Documentation\SAP\SHP633-302 SAP Final

1.0 17Apr2019.docx

Version Number: Version Date: Final 1.0 17Apr2019

Reference: CS WI BS005

Author:

Template No: CS TP BS016 Revision 4

Effective Date: 01Apr2016

- 1. If year and month are known, use the last day of the month.
- 2. If only year is known, use the last day of the year (31st December).
- 3. Otherwise, if stop date is unknown leave as missing.

6.4. INTERIM ANALYSES AND DATA MONITORING

An interim analysis of subjects 1-15 years of age will be performed at the completion of their participation.

Safety and tolerability results will be evaluated by a Data Monitoring Committee (DMC) which will convene approximately every 3 months during the active study period (date of the first subject's first dose to date of the last subject's last dose), based on subject enrollment. The DMC review will include all cumulative safety data from study assessment through the end of each review period.

6.5. MULTICENTER STUDIES

Because a small number of subjects are expected at each center, data from all centers will be pooled.

6.6. MULTIPLE COMPARISONS/MULTIPLICITY

Not Applicable.

6.7. ACTIVE-CONTROL STUDIES INTENDED TO SHOW EQUIVALENCE

Not applicable.

6.8. EXAMINATION OF SUBGROUPS

No subgroup analyses will be conducted given the small number of patients in this study.

7. Analysis Populations and Visits

If there are two populations that consists of the same patients, the analysis planned to be conducted for the two populations will only be conducted once for the intention-to-treat population and the analysis for the latter population (per protocol, safety and/or

Document: T:\Shire\Teduglutide\XXA39799\Biostatistics\Documentation\SAP\SHP633-302 SAP Final

1.0_17Apr2019.docx

Version Number: Version Date: Final 1.0 17Apr2019

Author:

Template No: CS_TP_BS016 Revision 4

Reference: CS_WI_BS005

Effective Date: 01Apr2016

pharmacokinetic) in this list will not be generated since it will be the same outputs.

7.1. SCREENED POPULATION

All subjects who provided signed Informed Consent Form will be included in the Screened population.

7.2. Intention-to-treat (ITT) Population

The intention-to-treat (ITT) population will consist of all subjects who are enrolled into the study. Subjects are considered enrolled in the study when they meet all eligibility criteria at screening and eligibility criteria are confirmed at visit 2/baseline. The ITT population will be the primary analysis population analyzed for efficacy/PD endpoints.

7.3. PER PROTOCOL (PP) POPULATION

The per protocol (PP) population will contain all subjects in the ITT population who complete the study treatment period without incidence of any major protocol deviations or other situations that could potentially affect the efficacy conclusion of the study.

Major protocol deviations leading to exclusion from the PP population include:

- Subjects with no detectable teduglutide post dose in the blood as part of PK assessments, or subjects who lack all PK assessments
- Missing baseline and/or Week 24 efficacy data
- Non-compliance to study drug as defined in Section 10

Major protocol deviations will be programmatically derived.

The Per Protocol population will be the sensitivity analysis population analyzed for primary efficacy endpoints. Reasons for exclusion from the PP population will be summarized for the ITT population and presented in the data listings.

7.4. SAFETY POPULATION

The Safety population will consist of all subjects in the ITT population who receive at least 1 administration of investigational product with any safety follow-up. All safety analyses will be conducted on this population, unless otherwise specified.

All collected data will be included in the listings.

Document: T:\Shire\Teduglutide\XXA39799\Biostatistics\Documentation\SAP\SHP633-302 SAP Final

1.0_17Apr2019.docx Author:

Version Number: Final 1.0
Version Date: 17Apr2019

Reference: CS WI BS005

Template No: CS_TP_BS016 Revision 4

Effective Date: 01Apr2016

Copyright © IQVIA. All rights reserved.

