13. SAFETY EVALUATION

All safety evaluations will be conducted on the Safety population. By-visit summaries will include all protocol scheduled visits during the 24-week treatment period, EOT and Week 28 visit.

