13.1. EXTENT OF EXPOSURE

The extent of exposure is defined as the number of days on treatment, calculated as: (date of last dose - date of first dose) + 1.

The first dose date and last dose date will be based on the eCRF. The extent of exposure, the number of days that the dose was administered will be summarized. The number and percentages of subject will be tabulated for extent of exposure categorized into weeks (<4, 4-<12, 12-<24 and ≥24). Exposure summaries will be presented for the ITT and Safety populations.

The information related to the study drug training provided by the study physician will be listed for all subjects in the Safety population.

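### The Safety population is drawn from an ITT population defined by eligibility, so a child dosed without meeting or being confirmed on a criterion could be left out of all safety tables

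*SAP*

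**What the plan says.** SAP 7.2 sets the starting point: "The intention-to-treat (ITT) population will consist of all subjects who are enrolled into the study". It then says what enrolment means: "Subjects are considered enrolled in the study when they meet all eligibility criteria at screening and eligibility criteria are confirmed at visit 2/baseline".

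SAP 7.4 takes the Safety population from within that set: "all subjects in the ITT population who receive at least 1 administration of investigational product with any safety follow-up". The same section adds "All safety analyses will be conducted on this population, unless otherwise specified", and SAP 13 repeats the rule with no exception: "All safety evaluations will be conducted on the Safety population". The one safety summary that names a further population is exposure, in SAP 13.1: "Exposure summaries will be presented for the ITT and Safety populations".

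Two statements cut the other way. SAP 7.4 also says "All collected data will be included in the listings", and SAP 6.4 says "The DMC review will include all cumulative safety data from study assessment through the end of each review period".

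The PK population is defined twice. SAP 7.5 takes it from the Safety population. Section 6 of the PK analysis plan starts instead from enrolled subjects with at least one injection and usable PK data, and sets no follow-up condition.

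**The concern.** A safety set is meant to describe what happened to the subjects who were exposed. Here membership depends first on eligibility and only then on exposure. If a child is dosed and eligibility was not met or not confirmed, the definitions give no route into the safety tables. Adverse event incidence, markedly abnormal laboratory counts, antibody results and exposure would then describe fewer children than were treated. In a purely descriptive study with cohorts this small, one child visibly changes every percentage.

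The table that ought to show such a case would miss it too: SAP 8.3 summarises protocol deviations on ITT.

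**Working it through.** There is no plan figure to reproduce. The check is of the nested definitions, followed by a simple share.

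**Set logic**

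1. ITT = enrolled (SAP 7.2).
2. Enrolled = all criteria met at screening and confirmed at visit 2/baseline (SAP 7.2).
3. Safety = part of ITT, with at least one dose and some safety follow-up (SAP 7.4).
4. So a child who does not satisfy step 2 is outside ITT and outside Safety, even if dosed.

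**Which outputs lose the child, on the literal reading**

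- All SAP section 13 summaries: these use Safety. Exposure adds ITT, but ITT carries the same eligibility condition, so the exception wording in 7.4 does not help.
- Protocol deviations (SAP 8.3): ITT.
- Disposition (SAP 8.4): ITT, PP, PK and Safety, all of which sit inside ITT under the SAP's definitions.
- Population counts (SAP 8.2): the child appears only in the Screened denominator.

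**Which outputs keep the child**

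- Listings, under the general statement in SAP 7.4. The wording is not uniform: SAP 13.6 limits the physical examination listing to Safety, and SAP 13.1 limits the drug-training listing in the same way.
- DMC review (SAP 6.4), which states no population restriction.

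**Size**

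Section 5 of the PK analysis plan gives planned enrolment of at least 5 children and at least 2 infants. These are enrolment figures. If the child in question is not enrolled, that child comes on top of them. Assume every enrolled child is dosed and there is one such case.

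Share of exposed subjects left out = 1 / (enrolled minimum + 1):

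- Children: 1 / (5 + 1) = 1/6 = 16.7%
- Infants: 1 / (2 + 1) = 1/3 = 33.3%
- Overall: 1 / (7 + 1) = 1/8 = 12.5%

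Because 5 and 2 are minimums, a larger enrolment makes each share smaller. With no such child, each share is 0. These are shares of the whole cohort. The documents do not give the number of children who began treatment after protocol amendment 3.0, so no share is calculated for that column.

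**The follow-up condition**

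Suppose 5 children are dosed, 1 has an event, and another has no safety follow-up. Counting all dosed children gives 1/5 = 20%. Dropping the child without follow-up gives 1/4 = 25%. The condition raises the reported incidence. If that child was eligible, the child also stays in the ITT exposure summary.

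**The case against.** The strongest reply is that SAP 7.2 describes a step taken at the site. Eligibility is checked at screening and confirmed at visit 2, and at that moment the child is enrolled. The SAP has no rule for removing a child from ITT afterwards. On this reading, a child who is confirmed, dosed and later found to fail a criterion stays in ITT and in Safety, and only a child dosed without confirmation falls out. This reading is tenable and narrows the gap. It does not close it, and the SAP does not say which reading applies, so two programmers could build different safety sets.

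The second reply also stands in part. The listings and the DMC still carry the child's data, and in a study this small individual listings hold much of the safety information. But neither puts the child into a reported count or percentage.

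A reader might go further than the documents allow in three ways:

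- **That the share is 1 of 5 or 1 of 2.** This counts the child among the enrolled, while the argument depends on the child not being enrolled.
- **That harm is understated because such children are at higher risk.** The eligibility criteria are not in these documents, and nothing in them shows that failing one raises risk.
- **That the follow-up condition hides harm.** As shown above, it shrinks the denominator and pushes incidence up.

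**Conclusion.** The point holds as a defect of definition. Taken literally, SAP 7.2 and 7.4 together leave a child dosed without meeting or being confirmed on a criterion out of all safety, exposure, disposition and deviation tables. On the lenient reading, this is confined to children dosed without confirmed eligibility. Neither reading supports saying that the child's data disappear, since listings and DMC review remain.

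At the planned minimum, one such child is at most 17% of exposed children or 33% of exposed infants, assuming all enrolled children are dosed. The effect is zero if the situation never arises. The direction of any bias in reported incidence cannot be stated, because it depends on what happens to that child. The case for changing the text is that a population definition has to be settled before anyone knows whether such a child exists, and that the change costs almost nothing.

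**What to change.** - **SAP 7.4:** define the Safety population as every subject who receives at least one dose of investigational product, whatever the subject's ITT membership or eligibility status.
- **Same sentence:** remove the follow-up condition, which the SAP does not define. This is a minor tidy-up so that every exposed child is counted; it does not correct understated harm.
- **PK population:** base it on the revised Safety population in SAP 7.5, and align section 6 of the PK analysis plan, which speaks of enrolled subjects and would not be reached by a change to the SAP alone.
- **SAP 14:** it currently reports no change from the protocol. The protocol is not at hand; if it uses the nested definition, record the change there.

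The cost is a few sentences across two documents. No new data are needed, and no table changes unless such a child occurs or a dosed child has no safety follow-up.
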